5.1 Flow Diagram

- The flow diagram will include, but not be limited to, the following:
 - Number of screened patients
 - Summary of reasons not enrolled
 - Number of enrolled participants by arm
 - Summary of off-treatment and off-study reasons
 - Number of participants in primary and secondary analysis populations.

5.2 Accrual

- Summary of participants enrolled by month (and arm).
- Summary of participants enrolled by site (and arm).

5.3 Baseline Characteristics

The following characteristics (day 0) will be summarized by arm

- Summary of age, sex, race, and ethnicity.
- Summary of body weight and body mass index (BMI).
- Summary of plasma HIV-1 RNA (number below lower limit of quantification and, for participants with detectable viral load, statistical summary of \log_{10} copies); ARV regimen.

5.4 Study Retention

- Summary of off-study reasons.

5.5 Study Treatment

- Summary of reasons for not starting study treatment.
- Summary of days from study entry to first dose of study drug.
- Summary of days from study entry to permanent discontinuation of study drug.
- Summary of the reasons for permanently discontinuing study drug, sorted so discontinuations due to treatment-related AEs are together.

5.6 Pregnancies (If Any)

- Summary of women who become pregnant while on study, including weeks from study entry, pregnancy outcome if known, and maternal AE if any. (Safety analysis population.)

5.7 Mortality (If Any)

- Summary of the number of deaths and the primary and contributing causes of death, with weeks from study entry. (Safety analysis population.)

5.8 Primary Analysis Results

- Descriptive summary of DTG PK parameters (C_{\max} , AUC_{0-24h} , and C_{\min}) at each of the two PK intensive time points, by arm. (Primary analysis population.)
- Geometric mean ratios of DTG PK parameters (C_{\max} , AUC_{0-24h} , C_{\min}), day 28 relative to day 0, and associated 90% CIs, by arm. (Primary analysis population.)

5.9 Secondary Analysis Results (Safety, Tolerability, Day 28 Viral Load)

- Summary of all new, post-entry reportable AEs by MedDRA high-level term and grade occurring during administration of DTG with 1HP, by arm. (Safety analysis population)
- Summary of SAEs by MedDRA code, by arm. (Safety analysis population)
- Discontinuation of study drugs during DTG and 1HP dosing, by arm (study drugs to include RPT, INH, DTG and NRTIs). (Safety analysis population)
- Discontinuation of study during DTG and 1HP dosing, by arm. (Safety analysis population)
- HIV-1 RNA levels >50 copies/mL at Day 28 (-2/+14 days) and/or at the Follow Up visit. (Safety analysis population)
- Analyses done for the Safety Analysis Population. Proportion of participants exhibiting each event is reported, along with the associated exact, 95% Clopper-Pearson binomial confidence intervals (CIs). For the AEs, each participant is counted only once, in the highest grade observed for the participant.

6 Calculation of geometric mean ratio and associated confidence interval

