3.0 STUDY DESIGN

A5372 is an open-label, two-arm, multicenter PK study to investigate the potential interactions between DTG and steady state RPT when RPT is given with INH daily for 4 weeks (1HP) in individuals living with HIV-1 and LTBI.

The majority of participants will be on study for 6 weeks (a 4-week on-study treatment period and a 2-week follow-up period). The duration may be up to 8 weeks as participants will have up to 6 weeks from enrollment to complete 4 weeks of treatment. Participants who are required to return for confirmation of virologic failure within 1 to 3 weeks after the follow-up visit may be on study for up to 11 weeks.

Initially, the study will begin enrollment with Arm 1. Once PK data are available from Arm 1 with at least 32 evaluable participants (participants with at least 6 plasma sample collections on each of the two intensive PK visits [6 of these collections must include 23- and 24-hr time points (trough levels) to ensure PK laboratory analysis can occur on at least 32 participants]), the clinical management committee (CMC) team and the SMC will review the DTG BID PK data to ensure sufficient plasma exposures of DTG (C_{trough}) are achieved with twice-daily DTG dosing. Upon review of the Arm 1 PK data, the PK data will be used to model the anticipated PK of QD DTG when co-administered with 1HP. Based on these models and simulations of QD DTG dosing with 1HP, a decision will be made on whether to open Arm 2 for enrollment. Refer to [section 7.4](#) for details on criteria for opening of Arm 2.

Plasma PK profiles for DTG will be determined at two time points. At the first time point, plasma samples will be drawn in participants at steady state with respect to DTG when receiving once daily DTG prior to 1HP. At the second time point, DTG will be given BID in Arm 1 and QD in Arm 2 during the 1HP LTBI regimen and PK sampling for DTG will occur on Day 28 of the 1HP regimen. In addition, sparse PK sampling will be performed on days 3, 14, and 21 of the 1HP regimen. Remaining plasma from the DTG analysis will be used to determine RPT concentrations achieved from 1HP dosing to support exploratory study objectives.

The study regimen will be as follows starting on Day 1 continuing through Day 28.

Arm 1

- DTG 50 mg orally BID (~12 hours apart)
 - 1st dose: DTG 50 mg each morning from non-study ARV supply
 - 2nd dose: DTG 50 mg each evening from study supply
- 1HP: INH 300 mg + RPT 600 mg orally each morning for 4 weeks

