6.2.3 Post-Entry Evaluations

On-Treatment Evaluations

Day 3

A study visit including sparse PK sampling will occur on Day 3 with a window of ± 2 days.

Day 14

A study visit including sparse plasma PK sampling will occur on Day 14, with a window of ± 2 days.

Day 21

A study visit including sparse plasma PK sampling will occur on Day 21, with a window of ± 2 days.

PK sampling at Day 3, Day 14, and Day 21 may only occur after ensuring 3 days of consecutive dosing of ART and/or RPT/INH prior to study visit. This will be recorded per participant self report.

Day 28

A study visit including intensive PK sampling will occur on Day 28 (window -2/+14 days).

PK sampling at Day 28 may only occur after ensuring 3 days of consecutive dosing of ART and RPT/INH prior to study visit (participant self report is sufficient).

NOTE: Participants will have 6 weeks to complete 4 weeks of on-study treatment.

Day 42

A follow up study visit should occur approximately 14 days following the completion of study treatment. The window for the day 42 follow-up visit is -2/+14 days.

NOTE: The timing of the day 42 visit may vary for some participants as participants will have up to 6 weeks from enrollment to complete 4 weeks of treatment.

Event-Driven Evaluations**Day 49 Confirmation of Suspected Virologic Failure**

Participants with plasma HIV RNA > 50 copies/mL at the Day 42 follow-up visit will return for a confirmatory plasma HIV RNA measurement approximately 7 days after the original sample collection or as soon as testing results are available.

At non-US sites, an additional plasma sample will also be collected for possible resistance testing, if viremia is confirmed. At US sites, the confirmatory sample should be sent to reflex for resistance testing if HIV viremia is confirmed, where feasible. If not feasible, an additional plasma sample for resistance testing should be collected at time of confirmation of viremia. Resistance testing should include integrase and reverse transcriptase resistance.

The window for the day 49 confirmation of suspected virologic failure visit is +28 days.

NOTE: The timing of the day 49 visit may vary for some participants as participants have up to 6 weeks from the time of enrollment to complete 4 weeks of treatment.

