6.3.4 Clinical Assessments

Complete Physical Exam

A complete physical examination will be performed at Screening only and is to include, at a minimum:

- examination of the skin, head, mouth, and neck
- auscultation of the chest
- cardiac exam; abdominal exam
- examination of the lower extremities for edema
- signs and symptoms
- diagnoses
- height (**in cm**)
- weight (**in kg**); **calculated** body mass index
- vital signs (temperature, pulse, respiration rate, and blood pressure)

Targeted Physical Exam

Targeted physical examination will be performed at all visits after Screening (except for on Day 1) and is to be driven by any previously identified or new signs or symptoms including diagnoses or adverse events that the participant has experienced since the last visit.

The exam must include:

- vital signs (temperature, pulse, respiration rate, and blood pressure)
- weight (**in kg**)

Refer to [section 7.2](#) for AE collection requirements.

Concomitant Medications

After entry, any new and discontinued concomitant medications must be recorded on the eCRFs.

Study Treatment Modifications

After entry, record all study drug modifications, including initial doses, participant-initiated and/or protocol-mandated modifications, **and** inadvertent and deliberate interruptions since the last visit. **All interruptions of study-supplied drugs, regardless of duration, must be recorded.** Record any permanent discontinuation of treatment. **Interruptions to non-study ART will be recorded on the concomitant medications log.**

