7.0 ADVERSE EVENTS AND STUDY MONITORING

7.1 Definition of Adverse Event

An adverse event (AE) is any unfavorable and unintended sign (including an abnormal laboratory finding), symptom, or diagnosis that occurs in a study participant during the conduct of the study regardless of the attribution (i.e., relationship of event to medical treatment/study product/device or procedure/intervention). This includes any occurrence that is new in onset or aggravated in severity or frequency from the baseline condition.

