10.2.2 Secondary Outcome Measures

- 10.2.2.1 Proportion of participants with all adverse events meeting the reporting criteria in [Section 7.2](#) during administration of DTG with 1HP, by arm.
- 10.2.2.2 Proportion of participants who discontinue study or study drugs during DTG and 1HP dosing, by arm.
- 10.2.2.3 Proportion of participants with HIV-1 RNA levels >50 copies/mL at Day 28 (-2/+14 days) and/or at the Follow Up visit.

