3.2 Secondary Outcome Measures

The secondary outcome measures for addressing the study’s secondary objectives are listed in protocol Section 10.2.2 as:

1. Proportion of participants exhibiting each of the following events during administration of DTG with 1HP, by arm [Outcome Measure 10.2.2.1]
 - a. Grade 3 adverse event(s) (AE(s))
 - b. Grade 4 AE(s)
 - c. Grade 3 or 4 AE(s)
 - d. AEs of grade 2 or higher
 - e. AEs that led to a change in study treatment regardless of grade
 - f. AEs meeting the serious adverse events (SAE) definition or EAE reporting requirements.
2. Proportion of participants who discontinue study or study drugs during DTG and 1HP dosing, by arm [Outcome Measure 10.2.2.2]. This includes discontinuation of DTG, RPT, INH, and NRTIs.
3. Proportion of participants with HIV-1 RNA levels >50 copies/mL at day 28 (-2/+14 days) and/or at the Follow Up visit [Outcome Measure 10.2.2.3].

4 Statistical considerations

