
IE: Failure to take DTG as prescribed (1) for 3 days prior to starting 1HP (Principal Stratum strategy)
 
IE: Failure to take DTG (1) and 1HP (2) as prescribed prior to steady state (Principal Stratum strategy)
 
(1) 6 BID 50 mg doses (Arm 1) or 3 QD 50 mg doses (Arm 2)
 
(2) 3 QD doses of 300 INH mg and 3 doses of 600 mg QD doses of RPT
 
For both intercurrent events the Principal Stratum is defined as having taken DTG and 1HP treatment as prescribed
	
Missing data may occur because of:
 
 Failure to appear at study visit (Day 0 or Day 28) Incomplete sampling (≥ 6 timepoints including both 23- and 24-hour samples) Incomplete/unevaluable concentrations when sampled (≥ 6 timepoints including both 23- and 24-hour samples) 
Missing samples and PK concentrations for participants otherwise meeting the dosing criteria will be assumed missing completely at random and participants excluded from the analysis.

Population-level summary measure	Analysis approach
Geometric mean ratio of DTG Cmax, Cmin, and AUC _{0-24h} with (after initiating 1HP; numerator) and without (prior to initiating 1HP; denominator) 1HP	Geometric mean ratio with associated 90% CIs. See Section 8 for details.

Sensitivity Analyses

No sensitivity analyses are planned.

Supplementary analyses

No supplementary analyses are planned.

4.9 Analysis Addressing the Safety, Tolerability and Virologic Suppression Secondary Objectives (Conducted by Statisticians)

For the Safety Analysis Population (see Section 4.2.3), proportions of the events listed in **Section 3.2** will be reported by arm: (a) the proportion of participants with Grade 3 or 4 AE during administration of DTG with 1HP; (b) the proportion of participants who discontinue study or study drugs during administration of DTG with 1HP; and (c) the proportion of participants with HIV-1 RNA levels >50 copies/mL at the second intensive PK measure and/or at the Follow Up visit. Proportions will be reported along with 95% exact Clopper-Pearson CIs around the proportions.

5 Report components

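### Non-serious adverse events that start after the last 1HP dose are collected but enter no planned AE proportion or AE table

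*SAP*

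**What the plan says.** Four places tie AE counting to the dosing period.

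- Protocol 10.2.2.1 defines the AE outcome as events "during administration of DTG with 1HP, by arm".
- SAP 3.2 item 1 plans the "Proportion of participants exhibiting each of the following events during administration of DTG with 1HP, by arm". Sub-items a to f sit under this limit, including f, which covers SAEs.
- SAP 4.9(a) plans to report "the proportion of participants with Grade 3 or 4 AE during administration of DTG with 1HP".
- SAP 5.9 plans a "Summary of all new, post-entry reportable AEs by MedDRA high-level term and grade occurring during administration of DTG with 1HP, by arm".

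Observation runs longer than dosing. Protocol 3.0 states: "The majority of participants will be on study for 6 weeks (a 4-week on-study treatment period and a 2-week follow-up period". Protocol 6.2.3, under Day 42, states: "A follow up study visit should occur approximately 14 days following the completion of study treatment". Protocol 6.3.4 states: "Targeted physical examination will be performed at all visits after Screening (except for on Day 1"; that examination is driven by signs, symptoms, diagnoses or AEs since the previous visit. Protocol 7.1 defines an AE as something "that occurs in a study participant during the conduct of the study regardless of the attribution" and includes worsening of an existing condition. Protocol 7.2 sends every Grade 2 or higher event to the eCRF, with no dosing-period limit.

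Other safety items have no such limit: the SAE summary in SAP 5.9, the discontinuation reasons, pregnancies and deaths in SAP 5.5 to 5.7, and the halting rule in protocol 10.5.1 and SAP 2.5. The viral-load outcome (protocol 10.2.2.3, SAP 3.2 item 3) extends to the Follow Up visit.

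**The concern.** The first secondary objective is the safety of giving DTG-based ART with 1HP, and protocol 2.1.1 says that safety with daily rifapentine is not yet established. A reaction to a four-week course need not start before the last dose. The plan pays for a visit two weeks later and records what is found there, but leaves non-serious findings out of the AE results.

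The windows also differ within the plan. A related Grade 3 event in follow-up could count towards halting the study and yet be absent from the reported Grade 3 or 4 proportion. An SAE in follow-up would appear in the SAE summary but not in the SAE proportion. Two secondary outcomes reported together, AEs and viral load, would cover different periods without the reader being told.

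The end of the window is also not operationally defined. Protocol 5.2 allows 28 doses to be spread over up to 42 days, and protocol 8.4 describes situations in which study-supplied drugs are held. The SAP does not say whether an event that starts during a hold counts as occurring during administration.

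**Working it through.** **1. Reproduce the plan's durations.** Protocol 3.0 gives 4 weeks of treatment plus 2 weeks of follow-up: 4 + 2 = 6 weeks = 42 days. With up to 6 weeks to finish dosing: 6 + 2 = 8 weeks = 56 days. Both match the protocol.

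**2. Time outside the counting window, for a participant who completes dosing.**

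| Schedule | Dosing days | Follow-up days | Share outside window |
|---|---|---|---|
| Nominal | 28 | 14 | 14/42 = 33% |
| Dosing takes 42 days | 42 | 14 | 14/56 = 25% |

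**3. Where an event starting after the last 1HP dose is reported.**

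| Event type | AE proportions (SAP 3.2, 4.9) | Tables (SAP 5.6, 5.7, 5.9) |
|---|---|---|
| Non-serious, Grade 2 or higher | No | Not in the AE table |
| SAE | No (item 1f has the limit) | Yes, SAE summary |
| Death | No separate death proportion; item 1f has the limit | Yes, mortality summary |
| Pregnancy, with any maternal AE | Not an AE proportion | Yes, pregnancy summary |

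The first row is the gap. No section adds a post-dose window or a follow-up AE table.

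**4. Effect on a proportion.** Assume 36 participants in the safety population of an arm, which is the planned enrolment. One participant whose only qualifying event starts in follow-up is worth 1/36 = 2.8 points. Exact (Clopper-Pearson) 95% intervals, the method in SAP 4.9:

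- 0/36 = 0% (0 to 9.7%)
- 1/36 = 2.8% (0.1 to 14.5%)
- 2/36 = 5.6% (0.7 to 18.7%)

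**5. How likely is at least one such participant?** The documents give no late-onset rate, so the per-participant risk p over follow-up is an assumption. The chance is 1 − (1 − p)^36:

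| Assumed p | Chance of at least one in 36 |
|---|---|
| 1% | 30% |
| 2% | 52% |
| 5% | 84% |
| 10% | 98% |

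**6. Direction.** Every participant with an event in the on-1HP window also has one in the longer window. The on-1HP proportion can therefore only be equal to or lower than the proportion through follow-up.

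**The case against.** The strongest reply is that the limit is the protocol's own. The objective is the safety of co-administration, and co-administration ends with 1HP. Participants then continue the ART prescribed by their usual provider, so in Arm 1 a count through follow-up mixes two exposure states. An on-treatment window is a recognised, prespecified choice, and the SAP follows it faithfully. This stands. It is a reason to keep the on-1HP proportion as the defined outcome and not to call the SAP a departure from the protocol. It does not explain why delayed-onset events already collected should appear in no AE table.

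A second reply is that participants remain protected: the halting rule and the monitoring reviews are not confined to dosing. This also stands. The gap is in the reported results, not in oversight.

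A reader might infer more than the documents support:

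- **That the loss is greatest in participants who stop early.** They have no fixed two-week follow-up. Under protocol 8.1 they have discontinuation evaluations and leave the study; after related Grade 3 or 4 toxicity they leave once the event has fallen to Grade 2 or lower. An event that prompts stopping began on treatment and is counted under SAP 3.2 item 1e. SAP 5.9 counts each participant at the worst grade seen and states no cap at the stop date.
- **That only SAEs escape the limit.** Deaths, pregnancies and discontinuation reasons do too.
- **That a liver-enzyme rise at Day 42 is a clear example.** The readable part of the Schedule of Evaluations shows no laboratory rows, so a scheduled test at that visit cannot be confirmed.
- **That a third of AEs are lost.** The 33% is a share of calendar time on the nominal schedule.

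**Conclusion.** The point holds as a gap in reporting. Non-serious Grade 2 or higher events that start after the last 1HP dose are collected and then left out of every planned AE proportion and AE table, and the SAE proportion has the same cut-off. As an account of safety through the end of the study, the AE results are incomplete, and the omission can only lower the proportions.

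The number of events affected is unknown. What can be stated is the uncovered time for completers (14 of 42 days, or 14 of 56) and the weight of one participant (2.8 points, assuming 36 in the safety population). The chances in the last table of the working rest wholly on assumed risks. The change should be made before the AE tables are produced, but it does not undermine the protocol-defined outcome or the primary PK analysis.

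**What to change.** Keep the on-1HP proportions in SAP 3.2, 4.9 and 5.9 as the secondary outcome of protocol 10.2.2.1. Beside them, add a second column, with the same exact 95% intervals, that counts participants with an AE whose onset or worsening falls between the first 1HP dose and the follow-up visit, or off-study if earlier. State that days on which 1HP is held are included in this column, and state how such days are treated in the on-1HP column. Apply the second column to item 1f as well, so that the SAE proportion can be reconciled with the SAE summary.

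No new data collection is needed. The cost is one extra column, and a few follow-up events unrelated to 1HP will be included. Showing both columns lets the reader separate events on dosing from those that came later.

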6.1 Introduction

A log-normal distribution is often used for analyzing positive, right-skewed data, including AUCs and other concentrations-based pharmacokinetic parameters (C_T , C_0 , C_{max}) (Van Belle, 2002). For a variable X that is assumed to be log-normally distributed, we write $X \sim LN(\mu, \sigma)$; here, μ and σ are considered location and scale parameters, but do not denote expected value or variance. For log-normally distributed X , if a new variable Y is defined as the natural (base e) log of X , written $Y = \ln(X)$, then Y is normally distributed – written $Y \sim N(\mu, \sigma^2)$ – with mean (expected value) μ and variance σ^2 .

In order to exploit theorems that apply to normally distributed data (eg, sums and differences of normally distributed random variables are also normally distributed), analyses of PK parameters are often conducted on the log scale. For example, one might calculate and report the sample mean \bar{Y} and sample standard deviation s on the log scale, and use the standard formula:

$$(\bar{Y} \pm t_{1-\frac{\alpha}{2}, n-1} \frac{s}{\sqrt{n}}) \quad [1]$$

to estimate $100*(1 - \alpha)\%$ CI around the log-scale PK parameter. The question then arises of how to convert findings back to the original scale, the scale with which pharmacologists and others are most familiar.

In what follows, we define the sample mean and variance for the normally distributed, log-transformed PK parameter Y :

$$\bar{Y} = \sum_{i=1}^n \frac{Y_i}{n} \quad [2]$$

$$s^2 = \sum_{i=1}^n \frac{(Y_i - \bar{Y})^2}{n-1} \quad [3]$$

6.2 Geometric Mean (GM) and Associated CI

An approach to calculating a CI around the GM would be to exponentiate (take the antilogarithm of) the mean \bar{Y} and the CI endpoints (Equation [1]). This approach is standard in the literature, and it is the approach taken here.

6.3 Geometric Mean Ratio (GMR) and Associated CI

In assessing drug-drug interactions, pharmacologists and clinicians often characterize the effect of co-administered drug(s) (inhibitor or inducer; “perpetrator”) on the PK parameter of another, target, drug (substrate; “victim”) as the ratio of a PK parameter when measured under 2 different conditions.

Generally, the *numerator* of the ratio represents PK parameter of the target drug *when taken with the co-administered drug(s)*, and the *denominator* represents the target drug PK parameter when the target drug

is taken alone. Estimates near 100% indicate co-administered drug has no effect; estimates significantly below 100% indicate that the co-administered drug up-regulates the metabolism of target drug thereby decreasing systemic exposure to the target drug; and estimates significantly above 100% indicate that the co-administered drug down-regulates the metabolism of target drug thereby increasing exposure.

The geometric mean ratio (GMR) is used to estimate the effects of the interacting drug, with the corresponding CI providing inference. To estimate the ratio on the original scale, the sample mean and standard deviation on the log scale are used, along with the logarithmic identity $\log\left(\frac{B}{A}\right) = \log(B) - \log(A)$ [4].

